#### **4.2.6.4 Vital signs**

Summaries of vital signs data will include all data obtained until 30 days after the last dose of study treatment or the start of a subsequent therapy (including crossover treatment), whichever occurs first. Pulse rate, systolic and diastolic blood pressure, body temperature, respiratory rate and weight will be listed by patient and summarized using standard summary statistics for the absolute value and change from baseline at each visit.

#### **4.2.6.5 ECOG performance status**

Summaries of ECOG data will include all data obtained until 30 days after the last dose of study treatment or the start of a subsequent therapy (including crossover treatment), whichever

occurs first. The number (%) of patients fulfilling each ECOG performance status category will be presented for each visit.

#### **4.2.6.6 Electrocardiogram (ECG) data**

ECG details will be listed individually by patient.

#### **4.2.6.7 Physical examination**

Shift to maximum post-baseline value will be summarized by treatment arm.

#### **4.2.7 Demographics and baseline characteristics**

The following will be summarized for all patients in the FAS by treatment group:

- Patient disposition (including screening failures and reason for screening failure) both for randomized treatment and separately for crossover therapy. For crossover patients the end of study reason will be the same for both the original treatment period and the crossover treatment period, but reasons for end of treatment will be distinct for the treatment periods.
- Important protocol deviations by category, summarized overall by treatment arm
- Inclusion in analysis sets
- Demographics (age, age group [ $< 50$ ,  $\geq 50 - < 65$ ,  $\geq 65 - < 75$  and  $\geq 75$  years], sex, race and ethnicity),
- Patient characteristics at baseline (height, weight, BMI, BMI group, nicotine use [never, current, former], alcohol use [never, current, former])
- Stratification factors according to IRT/RTSM and eCRF data (ECOG performance status, Rai staging)
- Patient recruitment by region/country
- Medical history (past and current)
- Disease characteristics at baseline:
  - ECOG performance status according to the clinical database
  - Rai staging according to the clinical database
  - Time since original diagnosis to randomization (in months)
  - CIRS-G
  - Age  $\geq 65$  years,  $>18$  and  $<65$  years (creatinine clearance 30 to 69 ml/min, CIRS-G $>6$ )
  - Bulky disease [ $<5$ ,  $\geq 5$ , no measurable lymph nodes]
  - 11q deletion
  - 13q deletion
  - IGHV (mutated, unmutated)
  - Complex karyotype

- Beta-2 microglobulin ( $>3.5$  mg/L,  $\leq 3.5$  mg/L)
- Cytopenia (neutropenia  $ALC \leq 1.5 \times 10^9/L$ , anemia: Hemoglobin  $\leq 11$  g/dL, thrombocytopenia:  $PLT \leq 100 \times 10^9/L$ , all of the above, any of the above, none of the above)
- Prior PBC transfusion within 28 days before randomization
- Prior platelet transfusion within 28 days before randomization
- Constitutional symptoms (weight loss, fever, night sweats, fatigue, any of above)
- Creatinine clearance group ( $<60$  mL/min,  $\geq 60$  mL/min)
- Absolute lymphocyte count
- Absolute neutrophil count
- Platelet count
- Hemoglobin level.

The medications will be coded following AZ standard drug dictionary/WHO Drug dictionary as applicable.

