5.1 Inclusion criteria

Subjects are eligible to be included in the study only if all of the following inclusion criteria and none of the exclusion criteria apply:

Informed consent

- 1 Capable of giving signed informed consent which includes compliance with the requirements and restrictions listed in the informed consent form (ICF) and in this protocol
- 2 Provision of signed and dated, written informed consent form prior to any mandatory study specific procedures, sampling, and analyses

The ICF process is described in Appendix A 3.

Age

- 3 Men and women:
 - (a) ≥ 65 years of age **OR**

- (b) >18 and <65 years of age, provided that they meet at least one of the following criteria:
 - (i) Creatinine clearance 30 to 69 mL/min using the Cockcroft-Gault equation (iwCLL guidelines)
 - (ii) A score higher than 6 on the Cumulative Illness Rating Score-Geriatric (CIRS-G) ([Appendix F](#))

Type of subject and disease characteristics

- 4 ECOG performance status of 0, 1, or 2
- 5 Diagnosis of CLL that meets published diagnostic criteria ([Hallek 2018](#)):
 - (a) Monoclonal B-cells (either kappa or lambda light chain restricted) that are clonally co-expressing B-cell marker (CD19, CD20, and CD23) and CD5
 - (b) Prolymphocytes may comprise <55% of blood lymphocytes
 - (c) Presence of $\geq 5 \times 10^9$ B lymphocytes/L (5000/ μ L) in the peripheral blood (at any point since the initial diagnosis)
- 6 Active disease per IWCLL 2018 criteria that requires treatment, at least 1 of the following criteria should be met:
 - (a) Evidence of progressive marrow failure as manifested by the development of, or worsening of, anemia (hemoglobin <10 g/dL) and/or thrombocytopenia (platelets <100,000/ μ L)
 - (b) Massive (i.e., ≥ 6 cm below the left costal margin), progressive, or symptomatic splenomegaly
 - (c) Massive nodes (i.e., ≥ 10 cm in the longest diameter), progressive, or symptomatic lymphadenopathy

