 - (d) Progressive lymphocytosis with an increase of >50% over a 2-month period or a lymphocyte doubling time (LDT) of <6 months. LDT may be obtained by linear regression extrapolation of absolute lymphocyte count (ALC) obtained at intervals of 2 weeks over an observation period of 2 to 3 months. In subjects with initial blood lymphocyte counts of $30 \times 10^9/L$ (30,000/ μ L), LDT should not be used as a single parameter to define indication for treatment. In addition, factors contributing to lymphocytosis or lymphadenopathy other than CLL (e.g., infections) should be excluded.
 - (e) Autoimmune anemia and/or thrombocytopenia that is poorly responsive to standard therapy
 - (f) Symptomatic or functional extranodal involvement (e.g., skin, kidney, lung, spine).

- (g) B-symptoms documented in the subject's chart with supportive objective measures, as appropriate, defined as ≥ 1 of the following disease-related symptoms or signs:
 - (i) Unintentional weight loss $\geq 10\%$ within the previous 6 months before Screening
 - (ii) Significant fatigue (ECOG performance status 2 or higher; inability to work or perform usual activities)
 - (iii) Fevers higher than 100.5°F or 38.0°C for ≥ 2 weeks before Screening without evidence of infection
 - (iv) Night sweats for ≥ 1 month before Screening without evidence of infection
- 7 Meet the following laboratory parameters:
 - (a) Adequate bone marrow function independent of growth factor or transfusion support 1 week before assessment, as follows:
 - (i) Absolute neutrophil count (ANC) ≥ 750 cells/ μL ($0.75 \times 10^9/\text{L}$); ANC ≥ 500 cells/ μL ($0.50 \times 10^9/\text{L}$) in subjects with documented bone marrow involvement of CLL
 - (ii) Platelet count $\geq 50,000$ cells/ μL ($50 \times 10^9/\text{L}$); platelet count $\geq 30,000$ cells/ μL ($30 \times 10^9/\text{L}$) in subjects with documented bone marrow involvement of CLL
 - (b) Serum aspartate aminotransferase (AST) and alanine aminotransferase (ALT) $\leq 2.5 \times$ upper limit of normal (ULN)
 - (c) Total bilirubin $\leq 2.0 \times$ ULN, unless directly attributable to Gilbert's syndrome
 - (d) Estimated creatinine clearance of ≥ 30 mL/min using the Cockcroft-Gault equation (Appendix E)

Reproduction

- 8 Negative pregnancy test (urine or serum) for female subjects of childbearing potential prior to enrollment
- 9 Prior to the planned date of randomization for female subjects, at least 1 of the following criteria should be met:

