## LIST OF ABBREVIATIONS

Abbreviation or special term	Explanation
AE	Adverse event
AESI	Adverse event of special interest
ALC	Absolute lymphocyte count
ALT	Alanine aminotransferase
AST	Aspartate aminotransferase
ATC	Anatomical Therapeutic Chemical
BICR	Blinded independent central review
BOR	Best overall response
CI	Confidence interval
CLL	Chronic Lymphocytic Leukemia
CMH	Cochran Mantel Haenszel
CR	Complete response
CRi	Complete response with incomplete bone marrow recovery
CSP	Clinical Study Protocol
CSR	Clinical Study Report
CT	Computed tomography
CTCAE	Common Terminology Criteria for Adverse Events
DAE	Discontinuation of investigational product due to adverse events
DBL	Database lock
DCO	Data cut-off
DoR	Duration of response
eCRF	Electronic case report form
ECI	Adverse Events of Clinical Interest
EDR	Early discrepancy rate
CCI	
EoT	End of treatment
CCI	
CCI	
FAS	Full Analysis Set
HR	Hazard ratio

Abbreviation or special term	Explanation
HRQoL	Health related quality of life
ICH	International Conference on Harmonisation
IDMC	Independent data monitoring committee
ITT	Intention-to-treat
IVIG	Intravenous immunoglobulins
IRT	Interactive Response Technology
IWCLL	International Workshop on Chronic Lymphocytic Leukaemia
KM	Kaplan-Meier
LD	Longest diameter
MRD	Minimal Residual Disease
NA	Not applicable
NDA	New drug application
NE	Not evaluable
NTL	Non-target lesion
OSAE	Other significant adverse events
ORR	Overall response rate
OS	Overall survival
RTSM	Randomization and Trial Supply Management
PD	Progressive disease
PFS	Progression free survival
PK	Pharmacokinetics
PR	Partial response
PRL	Partial response with lymphocytosis
CCI	[REDACTED]
RDI	Relative dose intensity
SAE	Serious adverse event
SAP	Statistical Analysis Plan
SAS®	A commercially available integrated system of software products, commonly used for reporting and analysis of Clinical Studies
SD	Stable disease
SoA	Schedule of assessments

---

Abbreviation or special term	Explanation
TBL	Total bilirubin
TEAE	Treatment emergent adverse events
TL	Target lesion
TTNT	Time to next therapy
VAS	Visual analogue scale
WHO	World Health Organization

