**Table 6 Laboratory Variables**

AST	Total protein
ALT	Triglycerides
Alkaline phosphatase (ALP)	Cholesterol
Gamma glutamyl transferase (GGT)	Lactate dehydrogenase (LDH)
Hematologyb	
White blood cell (WBC) count with differential	Platelet count
Red blood cell (RBC) count	Absolute neutrophil count (ANC)
Hematocrit	Absolute lymphocyte count (ALC)
Hemoglobin	
Pregnancy Test (females of childbearing potential only)	
Urine human chorionic gonadotropin (hCG) or Serum $\beta$ hCG	
Hepatitis B and C Testingc	
HBsAg	Hepatitis B surface antibody (HBsAb)
Anti-HBc	Hepatitis C (hepatitis C virus [HCV]) antibody
Hepatitis B PCR (clinically indicated)	Hepatitis C PCR (clinically indicated)
Other Tests	
T/B/NK Cell Count	Serum immunoglobulin levels
$\beta$ 2-microglobulin b	
Cytogenetics and FISH Panel b,d	Genetic molecular prognostic molecules b,e

a In case a patient shows an AST or ALT  $\geq 3 \times$ ULN together with total bilirubin  $\geq 2 \times$ ULN please refer to CSP Appendix D 'Actions required in cases of increases in liver biochemistry and evaluation of Hy's Law,' for further instructions.

b These tests will be performed at the central laboratory.

c Hepatitis serology testing must include HBsAg, HBsAb, anti-HBc and hepatitis C (HCV) antibody. In addition, any patients testing positive for anti-HBc must have quantitative PCR testing for HBV DNA during screening and monthly thereafter. Monthly monitoring should continue until 12 months after last dose of study drug(s). Any patient with a rising viral load (above lower limit of detection) should discontinue study drug and have antiviral therapy instituted and a consultation with a physician with expertise in managing hepatitis B. Since IVIG may cause false positive hepatitis serology, monthly PCR testing is not required in patients who are currently receiving or received prophylactic IVIG within 3 months before study enrollment and have a documented negative anti-HBc test before the initiation of IVIG therapy. PCR testing should be performed when clinically indicated (eg, in the setting of rising transaminase levels). Patients with a known history of hepatitis C or who are hepatitis C-antibody positive should have quantitative PCR testing for HCV RNA performed during screening. No further testing is necessary if the PCR results are negative at screening.

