##### Sustained hematologic improvement

Sustained hematologic improvement is defined as hematologic improvement that persisted continuously for  $\geq 56$  days (8 weeks) without blood transfusion or growth factors. This sustained improvement requires that 1) two assessments meet the improvement criteria and are at least 56 days apart, 2) all assessment(s) with non-missing data between those two assessments must meet the improvement criteria, and 3) there is no concomitant use of blood transfusion/growth factor during this time period. The proportion of subjects achieving sustained hematologic improvement in the subset of subjects with cytopenia(s) at baseline, prior to subsequent anticancer therapy, will be summarized by treatment arm.

Cytopenia is defined as at least one of the following 3 criteria being met:

- Neutropenia:  $ANC \leq 1.5 \times 10^9/L$
- Anemia:  $Hgb \leq 11 \text{ g/dL}$
- Thrombocytopenia: platelet count  $\leq 100 \times 10^9/L$ .

Hematologic improvement in the subset of patients with cytopenia(s) is defined as follows for each parameter:

- Improvement to hemoglobin  $> 11 \text{ g/dL}$  from baseline or increase  $\geq 50\%$  over baseline.
- Improvement to platelet counts  $> 100 \times 10^9/L$  from baseline or increase  $\geq 50\%$  over baseline.
- Improvement to  $ANC > 1.5 \times 10^9/L$  or increase  $\geq 50\%$  over baseline.

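### SAP 4.2.7 defines baseline neutropenia by lymphocyte count (ALC), contradicting the neutrophil-count (ANC) definition in SAP 4.2.2.9

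*SAP*

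**What the plan says.** SAP 4.2.7 lists what is summarized at baseline for the full analysis set. One item, opening "Cytopenia (neutropenia", has three components: neutropenia, given as ALC ≤ 1.5 × 10^9/L; anemia, given as hemoglobin ≤ 11 g/dL; and thrombocytopenia, given as platelets ≤ 100 × 10^9/L. Three composite rows follow: "all of the above, any of the above, none of the above".

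SAP 4.2.2.9, under sustained hematologic improvement, sets out the same concept: "Cytopenia is defined as at least one of the following 3 criteria being met". Its criteria are ANC ≤ 1.5 × 10^9/L, hemoglobin ≤ 11 g/dL and platelets ≤ 100 × 10^9/L. The proportion with sustained improvement is then reported "in the subset of subjects with cytopenia(s) at baseline, prior to subsequent anticancer therapy".

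The SAP keeps the two analytes apart. Its abbreviation list expands ALC as "Absolute lymphocyte count". Table 6 lists "Absolute neutrophil count (ANC") as a separate variable from ALC. Section 4.2.7 also summarizes the two counts as separate baseline items further down the same list.

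**The concern.** A lymphocyte threshold cannot define neutropenia. The two sections agree on every cut-off and differ only in the analyte of one component, which points to ALC having been written where ANC was meant. SAP section 6, on changes from the protocol, does not explain the use of ALC. The amendment history records other revisions to 4.2.7 but says nothing on this point.

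What is at stake is a descriptive table. Baseline cytopenia describes disease burden by arm in the study report, and the same concept fixes the denominator of a planned efficacy summary. Under the literal text, one table would carry a neutropenia row that does not measure neutropenia, and its 'any' count could disagree with the subset size in another table of the same report.

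**Working it through.** There is no stated figure to reproduce, so the check compares the two rules and then works out which rows can differ.

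**Definitions side by side**

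| Component | SAP 4.2.7 | SAP 4.2.2.9 |
|---|---|---|
| Neutropenia | ALC ≤ 1.5 × 10^9/L | ANC ≤ 1.5 × 10^9/L |
| Anemia | Hb ≤ 11 g/dL | Hb ≤ 11 g/dL |
| Thrombocytopenia | PLT ≤ 100 × 10^9/L | PLT ≤ 100 × 10^9/L |

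The improvement rule in 4.2.2.9 is also written in ANC (above 1.5 × 10^9/L, or a rise of at least 50% over baseline).

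**Should the counts agree?** Section 4.2.7 uses the FAS. Section 4.2.2 uses the FAS for efficacy unless otherwise specified. With the same baseline record and no missing values, the 'any' count in 4.2.7 should therefore equal the size of the 4.2.2.9 subset.

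**Which rows change?** Call a patient discordant if exactly one of ANC and ALC is at or below 1.5. Concordant patients are classified identically under both rules. For discordant patients:

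| Other components at baseline | Rows that change |
|---|---|
| Neither anemia nor thrombocytopenia | neutropenia, 'any', 'none' |
| Exactly one of the two | neutropenia only |
| Both | neutropenia, 'all' |

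The anemia and thrombocytopenia rows never change.

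**Size of the mismatch.** Among patients with Hb > 11 and PLT > 100, let a be the number with ANC ≤ 1.5 and ALC > 1.5, and b the number with ANC > 1.5 and ALC ≤ 1.5. Then

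'any' count in 4.2.7 − subset size in 4.2.2.9 = b − a,

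and the 'none' count is off by a − b. The two outputs reconcile only if a = b.

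**Can such patients be enrolled?** Protocol 5.1 accepts ANC ≥ 0.75 × 10^9/L, and ≥ 0.50 × 10^9/L "in subjects with documented bone marrow involvement of CLL", so eligible patients can have ANC ≤ 1.5. Take ANC 1.0 and ALC 50 (both × 10^9/L), Hb 12 g/dL and PLT 150 × 10^9/L. The ANC exceeds 0.75, so the neutrophil criterion for entry is met. Under 4.2.7, 50 > 1.5, 12 > 11 and 150 > 100, so the patient is counted in 'none'. Under 4.2.2.9, 1.0 ≤ 1.5, so the patient belongs to the cytopenia subset. This patient adds 1 to a.

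**Likely direction.** Protocol 5.1 requires at least 5 × 10^9/L B lymphocytes "in the peripheral blood (at any point since the initial diagnosis" and active disease, and Protocol 5.2 excludes prior CLL-specific therapy. These make a > b the natural expectation: neutropenia, 'all' and 'any' too low, 'none' too high. The lymphocyte threshold need not be met at baseline, however, so the criteria do not bound b or give a value for a.

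**The case against.** The slip largely explains itself. The row is labelled neutropenia, a competent programmer would probably use ANC, and no table shell or program is available to show otherwise. Baseline ANC is summarized separately in any case. The cytopenia item is not a stratification factor or a listed PFS subgroup, and hematologic improvement is not among the formal analyses in SAP Table 7. Any wrong output is therefore conditional on literal implementation. All of this stands and keeps the point minor. It does not remove the contradiction: the SAP states a derivation rule, and the rule is wrong as written.

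The printed word could also be a conversion error in the available copy. That is unlikely, since ANC appears correctly in 4.2.2.9 and ALC is a defined term, but the signed SAP will settle it.

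Three stronger readings are tempting and are not supported:

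- A reader might infer that the neutropenia row would show about 0%. No baseline ALC distribution is given, and the entry threshold may have been met at any time since diagnosis.
- A reader might infer that the rows are wrong for all of the roughly 150 patients. Only discordant patients change, and for the composite rows only some of those.
- A reader might infer that the hematologic-improvement analysis is wrong. Section 4.2.2.9 carries its own complete ANC definition and does not draw on 4.2.7.

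**Conclusion.** The inconsistency is real and of the lowest severity. SAP 4.2.7 applies a lymphocyte criterion to neutropenia and contradicts SAP 4.2.2.9. If implemented as written, four baseline rows can be affected (neutropenia, 'all', 'any' and 'none'), and the 'any' count fails to match the 4.2.2.9 subset whenever a differs from b. The number of misclassified patients cannot be derived from the documents. The conclusion assumes that the text is implemented literally and that both outputs use the same baseline record. The anemia and thrombocytopenia rows, the 4.2.2.9 analysis, the primary PFS comparison, stratification, alpha and sample size do not depend on it.

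**What to change.** Replace ALC with ANC in the cytopenia item of SAP 4.2.7. Create one baseline-cytopenia derivation and use it for both the baseline table and the 4.2.2.9 subset, so that the counts reconcile by construction.

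The protocol synopsis says that the analysis at the 03Jan2024 cut-off was treated as final, so the table may already exist. Check which variable it used. If it used ANC, correct the text and note the erratum in the study report. If it used ALC, also rerun the four affected rows. The cost is one word in the SAP, one programming check and, only if needed, a rerun of part of a descriptive table.

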#### **4.2.8 Concomitant and other treatments**

Information on any treatment within the four weeks prior to initiation of study drug and all concomitant treatments given up to 30 days after discontinuation of study drug, or objective disease progression (whichever is later), with reasons for the treatment, will be recorded in the eCRF. Thereafter, only subsequent regimens of anti-cancer therapy will be recorded in eCRF.

Other anti-cancer therapies, investigational agents, and radiotherapy should not be given while the patient is on study drug.

Medications received prior to, concomitantly, or post-treatment will be coded using the WHODrug Dictionary Anatomical Therapeutic Chemical (ATC) Classification codes. Concomitant medications will be summarized for the FAS by ATC classification codes.

For the purpose of inclusion in prior and/or concomitant medication or therapy summaries, incomplete medication or radiotherapy start and stop dates will be imputed as detailed in [Section 4.2.4](#).

Prior medications, concomitant and post-randomized treatment medications are defined based on imputed start and stop dates as follows:

- Prior medications are those taken prior to study drug with a stop date prior to the first dose of study drug.
- Concomitant medications are those with a stop date on or after the first dose date of study drug (and could have started prior to or during treatment).
- Post-treatment medications are those with a start date after the last dose date of study drug.

In addition, all post-treatment anti-cancer therapies will be summarized for the full analysis set.

The following summaries will be produced:

- Summary of concomitant medications
- Summary of Post study drug cancer therapies

All concomitant and other treatment data will be listed.

Missing coding terms should be listed and summarized as "Not coded".

#### **4.2.9 Pharmacokinetic data**

Plasma concentrations of acalabrutinib and ACP-5862 will be summarized for the PK analysis set by nominal sample time using standard summary statistics for PK concentrations (geometric mean, geometric coefficient of variation, geometric mean  $\pm$  standard deviation, arithmetic mean, standard deviation, minimum, maximum and n). All plasma concentrations will be listed.

#### **4.2.10 COVID-19**

Additional analyses may be performed to explore the impact of coronavirus disease 2019 (COVID-19) on the safety and efficacy results reported for the study. The following may be explored:

- Safety data analysis separately for patients affected by COVID-19.
- Listing of protocol deviations related to COVID-19 and the reasons for the protocol deviation may be provided.

Sensitivity analysis on key efficacy endpoints may be performed if there is more than 10% of the total events are COVID-19 related. In these sensitivity analyses, any patient who had a death with primary or secondary cause as COVID-19 infection will be censored at their COVID-19 infection death date. COVID-19 deaths will be identified by primary/secondary cause of death.

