The survival follow-up will begin after BICR or investigator-confirmed progressive disease. During this phase the following information will be recorded: subsequent anti-CLL therapy including best response, IWCLL indication for treatment initiation, additional malignancy occurrence, and survival status. The survival follow-up will continue until death, lost to follow-up, consent withdrawal, or study closure, whichever occurs first.

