### **3. PRIMARY AND SECONDARY VARIABLES**

#### **3.1 Handling of crossover patients**

Patients in Arm B who have BICR-confirmed progression will have the option to crossover to acalabrutinib. For all efficacy analyses, except for the analysis of OS, will include data prior to crossover. OS will encompass the entire study duration.

All safety analyses, except that for death, will include data prior to crossover unless noted otherwise. Death will be summarized in the following three ways: over the randomized period, crossover period and entire study duration.

The crossover period is defined only for patients who were randomized and received at least one dose of crossover therapy.

Prior to crossover first/last dose refers to the first/last dose of chlorambucil/rituximab. Post crossover first/last dose refers to the first/last dose of acalabrutinib.

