## 3.3 Efficacy Variables

### 3.3.1 Progression free survival (PFS)

PFS is defined as the time period from the date of randomization until progression or death from any cause, whichever occurs first (i.e. date of PFS event or censoring – date of randomization + 1, time period is calculated in months). Patients who withdraw from the study or are considered lost to follow-up without prior documentation of disease progression will be censored on the date of the last adequate disease assessment. However, if the patient progresses or dies immediately after two or more consecutive missed response evaluations, the patient will be censored at the time of the latest adequate disease assessment prior to the two or more missed visits. Patients who start new anti-cancer therapy before documentation of disease progression will be censored on the date of the last adequate disease assessment that is on or before the start date of the new anti-cancer therapy. For patients without an adequate post-baseline disease assessment or no baseline assessments, PFS will be censored on the date of randomization unless they die within 2 visits of baseline. Detailed censoring rules are described below.

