**Table 4 Censoring rules for PFS**

Assessment	Outcome	Date of progression or censoring
Death before first response evaluation 	Event	Date of death
Documented PD between scheduled visits  (or, between a scheduled and unscheduled visit, if the unscheduled visit falls in between two scheduled visits) on or before receiving subsequent anti-cancer therapy or data cutoff, whichever occurred first	Event	Earliest date of disease assessment documenting progression
Death without documented PD  and not receiving subsequent anti-cancer therapy on or before data cutoff	Event	Date of death
No baseline tumor assessments and it's not known to have died in 2 consecutive visits of baseline. In cases of no measurable disease at baseline censoring will not occur.	Censored	Date of randomization
No adequate post-baseline response evaluations and is not known to have died in 2 consecutive visits of baseline	Censored	Date of randomization
Documented PD or death after subsequent anti-cancer therapy and the subsequent anti-cancer started before data cutoff date	Censored	Date of last adequate disease assessment prior to subsequent anti-cancer treatment
No documented PD or death at the time of data cutoff and subsequent anti-cancer therapy started before the data cutoff	Censored	Date of last adequate disease assessment prior to subsequent anti-cancer treatment
Documented PD or death after subsequent anticancer therapy and the subsequent anticancer started after data cutoff date	Censored	Date of last adequate disease assessment on or before data cutoff
No documented PD or death at the time of data cutoff and patient not received subsequent anticancer therapy or subsequent anticancer therapy started after the data cutoff	Censored	Date of last adequate disease assessment on or before data cutoff
Withdrew consent without documented PD or death	Censored	Date of last adequate disease assessment on or before date of withdrawn consent
Lost to follow-up without documented PD or death	Censored	Date of last adequate disease assessment on or before data cutoff
Documented PD or death after 2 or more consecutively missed response evaluations	Censored	Date of last adequate disease assessment before the consecutively missed visits

 Having not missed 2 consecutive response evaluations.

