#### **PFS sensitivity analyses**

The following sensitivity analyses will be performed:

- In addition to the stratified primary analysis the unstratified log rank test and unstratified hazard ratios will be calculated.
- The primary analysis will also be repeated without PFS censoring to subsequent therapies. Therefore, patients who receive a subsequent therapy prior to progression or death will be assigned an event time according to their recorded progression or death date. Patients who receive a subsequent therapy and did not progress or die will be censored according to the rules in table 4 other than the subsequent therapy rule.

- The primary analysis will be repeated except that the actual PFS event times, rather than the censored times, of patients who progressed or died in the absence of progression immediately following two, or more, tumor assessments will be included. This will be supported by a Kaplan-Meier plot of the time to censoring where the censoring indicator of the primary PFS analysis is reversed (what was originally a censored event in the primary PFS analysis becomes an actual event and what was originally a PFS event becomes a censored event) will be presented.
- Ascertainment bias will be assessed by analyzing the investigator data. The stratified log rank test will be repeated on PFS using the investigator data based upon IWCLL 2018. The HR and CI will be presented.
- Concordance between Investigator and BICR assessed progression will be presented for each treatment group.

If there is an important discrepancy between the primary analysis using the BICR data and this sensitivity analysis using investigator data then the proportion of patients with site confirmation but no central confirmation of progression will be summarized; such patients have the potential to induce bias in the central review due to informative censoring. An approach of imputing an event at the next visit in the central review analysis may help inform the most likely HR value ([Fleischer et al 2011](#)), but only if an important discrepancy exists.

The primary analysis may also be repeated using the randomization strata as entered into the database rather than those entered into the IVRS system, but only if the proportion of patients with a discrepancy is more than 10%.

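### SAP 4.2.10 defines COVID-19 censoring by patient, not by endpoint event, so read literally it can overwrite a progression or censoring that came before a COVID-19 death

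*SAP*

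**What the plan says.** SAP 4.2.10 allows an extra analysis if COVID-19 accounts for enough events: "Sensitivity analysis on key efficacy endpoints may be performed if there is more than 10% of the total events are COVID-19 related". The endpoints are not named. In these analyses, "any patient who had a death with primary or secondary cause as COVID-19 infection will be censored at their COVID-19 infection death date". The section makes no exception for a patient who had already progressed, started another therapy or been censored.

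The primary PFS derivation works by first event. SAP 3.3.1 runs the clock from "the date of randomization until progression or death from any cause, whichever occurs first". SAP Table 4 counts documented progression as an event, subject to its conditions on subsequent therapy and missed evaluations, and dates it at the "Earliest date of disease assessment documenting progression".

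Two further provisions matter:

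- Follow-up for death continues after progression. SAP 1.2 says: "The survival follow-up will begin after BICR or investigator-confirmed progressive disease".
- SAP 3.1 limits the data used for Arm B patients who move to acalabrutinib: "For all efficacy analyses, except for the analysis of OS, will include data prior to crossover". SAP 2.1 sets the same limit for analyses on the full analysis set, unless specified otherwise.

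**The concern.** A COVID-19 sensitivity analysis is meant to show what happens when deaths that became endpoint events because of COVID-19 are no longer counted as events. That calls for a rule about events. The rule in SAP 4.2.10 is about patients: once a patient has died of COVID-19, the death date becomes the censoring date.

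For OS the two kinds of rule coincide, because death is the only event. For PFS they differ whenever progression came first. PFS is the primary endpoint, so it is hard to see how the key efficacy endpoints could leave it out. A programmer who follows the sentence as written would remove a valid progression event and credit the patient with progression-free time after progression. A programmer who follows the probable intent would keep the event. The two would produce different event sets from the same SAP.

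**Working it through.** **1. The design figures reproduce (context only).** The inputs, from SAP 1.3 and 4.2.1, are HR 0.333, about 50 events, 1:1 allocation, two-sided alpha 0.05 and one interim at 38/50 events.

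- Schoenfeld power is Φ(√(50/4) × |ln 0.333| − 1.96) = 97.3%. With the two-look Lan-DeMets O'Brien-Fleming boundary it is 97.1%. The plan states more than 95%.
- The nominal alphas come out at 0.0203 and 0.0440. The plan states 0.02 and 0.044.

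Nothing in this point disturbs these figures.

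**2. The rules applied to one patient.** Take an Arm A patient, or an Arm B patient who did not cross over, with BICR progression at month 18 and a COVID-19 death at month 28.

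| Rule | Status | Time |
|---|---|---|
| SAP 3.3.1 and Table 4 | Event | Month 18 |
| SAP 4.2.10, literal | Censored | Month 28 |
| SAP 4.2.10, probable intent | Event | Month 18 |

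The literal rule loses one event and adds 28 − 18 = 10 months of progression-free time. In the same way, a patient censored earlier, for example at a new therapy or after two missed evaluations, would have that date moved forward to the death.

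**3. The same history after crossover.** If the Arm B patient crossed over between months 18 and 28, SAP 2.1 and 3.1 appear to keep the later death out of the PFS data, so the progression stands. SAP 4.2.10 does not say which provision takes precedence. If the pre-crossover limit does, crossed-over Arm B progressors keep their events while Arm A progressors lose theirs.

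**4. A COVID-19 death with no progression.** The rule censors at death. Most censoring rows in Table 4 use the last adequate disease assessment, and two use the date of randomization.

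**5. The trigger.** More than 10% of 48 events (the number the protocol synopsis reports at the 03Jan2024 cut-off) means more than 4.8, so at least 5. For 50 events it means more than 5, so at least 6. If total events means PFS events, a patient who progressed and later died of COVID-19 does not count towards the trigger, yet is caught by the literal rule. The trigger therefore does not bound the number affected.

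**6. Illustrative size.** The simulation used 2,000 runs with 75 per arm, exponential medians of 90 and 30 months, 30-month uniform accrual and a cut at month 53. It assumed no dropout, which gives 62.5 events on average, more than the planned 50. In k patients with an event, that event was recoded as censored 6 months later, or at the cut if earlier. Both k and the 6-month gap are assumptions.

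| k | All in Arm A | All in Arm B |
|---|---|---|
| 0 | 0.334 | 0.334 |
| 1 | 0.315 | 0.343 |
| 3 | 0.278 | 0.362 |
| 5 | 0.240 | 0.384 |

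A rough check uses the expected events per arm at month 53, which are 18.9 in Arm A and 43.2 in Arm B. For k = 5, 0.334 × (18.9 − 5)/18.9 = 0.246 and 0.334 × 43.2/(43.2 − 5) = 0.378. Both are close to the simulated values.

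The table puts all affected patients in one arm, which is the extreme case. A second illustration assumed COVID-19 mortality of 6–15% in study months 33–37, unrelated to arm or progression, with a cut at month 45. The literal rule then deleted about 4–8% of PFS events, and the mean HR moved only from 0.33 to about 0.334. That run applied the rule to every patient who died of COVID-19 and ignored the pre-crossover limit.

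**The case against.** The best answer is that the literal reading is not the intended one. The preceding sentence of SAP 4.2.10 speaks of COVID-19-related events, so the rule can be taken to say how those events are treated. A sensitivity analysis changes the primary derivation only where it says so, and once a patient has progressed, a later death is not a PFS outcome. That is probably what was meant, and the first-event definition in SAP 3.3.1 supports it. But SAP 4.2.10 does not say it. Elsewhere the SAP is explicit: in the analysis that lifts censoring for subsequent therapy, affected patients "will be assigned an event time according to their recorded progression or death date". The COVID-19 section has no equivalent wording.

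The crossover provisions are a second answer. They appear to protect Arm B patients who crossed over, but not Arm A progressors or Arm B progressors who stayed off crossover.

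The objections to the reach of the point also stand. Neither document calls DoR or TTNT key, so their inclusion cannot be assumed. For a COVID-19 death without progression, the choice between the death date and the last assessment is partly a matter of convention, and no effect of it has been shown.

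**Conclusion.** The point holds as a wording defect with limited consequences. SAP 4.2.10 states a patient-level rule which, followed literally for PFS or for any other non-OS endpoint treated as key, contradicts the first-event definition and Table 4.

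Three stronger conclusions might be inferred, and the documents do not support them:

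- **A known direction of bias.** One might expect the rule to remove more Arm B progressions, because Arm B is assumed to progress faster. The pre-crossover limit may reverse this, and precedence is not stated. The direction depends on which arm loses events and is not established.
- **A threat to the trial's conclusion.** The primary PFS test, its alpha and the success criterion are untouched. The COVID-19 analysis is optional, conditional and supportive.
- **A known size.** The documents give no COVID-19 death counts. The range 0.240–0.384 rests on assumed numbers of patients, all placed in one arm. With COVID-19 deaths unrelated to arm or progression, and the pre-crossover limit ignored, the average shift was small.

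**What to change.** In SAP 4.2.10:

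- Name the endpoints covered.
- State that a patient is censored only where the COVID-19 death is itself the endpoint event: at the death date for OS, and at the last adequate disease assessment before death for PFS, in line with most Table 4 censoring rows.
- State that earlier progression or next-therapy events, and earlier censoring dates, stand as in the primary derivation.

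If DoR or TTNT is named, give its censoring date in the same place.

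The cost is two or three sentences and no new data. The protocol synopsis records that the 03Jan2024 cut-off was treated as the final analysis and the study unblinded. The change should therefore be dated and recorded as a clarification, with the clinical study report stating which derivation was used if the analysis was run.
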